symptomatology in TS. Because synchronized gamma oscillations are a fundamental property of thalamocortical communication and DBS therapy, we will perform a comprehensive study of the modulations to define the relationship between gamma oscillations and tic expression in cortical and subcortical targets. In order to accomplish this goal, we will use a DBS system that utilizes an implanted programmable neurostimulator that will allow for synchronized recording of cortical and subcortical LFPs, and consequently enable the investigation of tic-related brain oscillation dynamics. This avenue of research is the first critical step in neurosensing and responsive neuromodulation. The neurostimulator (Medtronic Summit RC+S device and cortical ECOG strips (Model 09130) is novel in that it can be programmed to provide continuous or responsive stimulation. Both deep brain and cortical ECOG strips will be placed as part of this system. We will collect real time, local field potentials (LFPs) that are time synchronized with clinical behavior, and we will collect these from both the CM region and from pre-motor and motor cortex in order to study thalamocortical interactions in the context of human TS. The collection of these potentials will allow us to better understand the fundamental neural activity important to tic generation (specific aim 2), and to attempt responsive stimulation approach (specific aim 3). Our proposal will uncover the neuronal activity inherent to CM and from cerebral cortex, and will reveal how DBS affects this activity in the human TS patient.

(3) Test the hypothesis that responsive brain stimulation will provide an alternative to chronic deep brain stimulation in TS. We hypothesize that we will be able to use physiological changes collected in Specific Aim 2 to tailor a responsive

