therapy for TS patients. This paradigm is preferable to chronic stimulation for its potential to reduce stimulation-related side effects. Outcomes will be measured by comparing the results of chronic continuous stimulation (Specific Aim 1) to an acute test of responsive stimulation (Specific Aim 3). Responsive stimulation parameters will be identical to chronic continuous stimulation parameters and will strictly be within safety ranges. If acute responsive stimulation leads to low side effects and comparable clinical outcomes for a patient, we will test chronic responsive stimulation for one week at a time, up to four weeks in total. This procedure will be performed at an appropriate time point (approved by the Principal Investigator) after the 6 month primary endpoint is reached but prior to Month 36 (study completion) (see visits 6.1-6.4 in schedule of events). The patient programmer will allow patients to turn off responsive stimulation and switch back to standard continuous therapy. A firmware update from Medtronic will allow the Summit RC+S internal signal sensing and processing units to communicate with the stimulation unit. Outcomes for chronic responsive stimulation will also be measured by comparing the results of chronic continuous stimulation.

Duration of the Investigation: We expect the duration of this investigation will be five years. In the first year we plan to implant and follow the first two subjects. In Year 2 we will plan to implant and follow the third, fourth, and fifth subjects while we continue to follow the first two subjects. In Year 3 we plan to implant and follow the sixth and seventh, and eighth subjects while we continue to follow the first five subjects. In Year 4 we plan to implant and follow the ninth and tenth subject, but also to continue to follow the other eight subjects. In Year 5 we will complete follow-up

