- Physiology data beyond month 12, and the chronic stimulation titration (visits 6.1-6.4), may be performed at the participant’s home as necessary rather than at the University of Florida. The equipment used are all mobile as shown in the RC+S system configuration as explained in Section 18 (refer to Figure 3).
- Details of physiology collection procedure: The subject will be asked to put on EMG sensors and signals from this device will stream into the research host computer (RHC). The signals from the Summit RC+S device will also be downloaded onto the RHC, which will have the Summit Research

Development Kit (RDK) installed (refer to Section 19). Stimulation and brain activity data since the previous visit can then be reviewed and analyzed on an individual basis.

- The CM neurostimulators will be programmed in an outpatient setting to deliver only chronic continuous stimulation in all patients. Stimulation parameters will be adjusted as necessary to provide maximal tic reduction. The cortical strips will be chronically set to record mode for data collection only, until the acute Aim 3 responsive trial.
- The neurologist and DBS programmer will be allowed to adjust stimulation parameters during months 1-5 to achieve maximal tic suppression and minimal to no side effects. The programming that will be employed will be identical to that used for Parkinson's disease randomized trials[13, 67-71].
- At day 180 (6 months +/- 14 days), the primary and secondary outcome variables will be collected, as will all scales. If optimization is not achieved at Month 6, Month 6 data collection may be postponed as deemed necessary by the Principal Investigator (with the exception of the C-SSRS), up to 12 months (+/- 14 days) past the first programming visit (Month 1). However, there must be a 30 period of stable stimulation settings before primary outcomes are assessed.
- Primary and secondary outcomes and physiology collection will be assessed over approximately 3 outpatient days. The "on" DBS condition will be used and compared to the pre-operative baseline for the primary outcome (specific aim 1). The other conditions will be used for secondary analyses, and the on

responsive stimulation response will be compared to the pre-operative baseline (specific aim 3).

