binomial test. We will compare the baseline motor YGTSS to the on DBS condition at six months (primary outcome). We will also perform comparisons of baseline to on/off/responsive conditions, and also comparisons of on/off conditions at six months as secondary analyses. To compare on versus off condition, we will form paired difference scores of YGTSS (YGTSS on minus YGTSS off) at six months and test for significance using the Wilcoxon signed rank test.

Specific Analysis Approach for Aim 2: We will first investigate rate and pattern changes in physiology and the possible correlation with clinical manifestation of motor tics by using exploratory data analysis techniques that will be graphical in nature. These exploratory techniques will include spectrograms and event related potentials. We will then conduct a preliminary time series analysis estimating fractal dimension, line length, and area-under-the-curve of the raw signal. The data obtained from these analyses will inform subsequent analysis and guide the development of statistical methods to analyze these types of data streams. Subsequent analysis will be more comprehensive, and will include time-frequency analysis of specific frequency bands, measures of coherence between channels containing movement related activity, and quantification of phase-amplitude coupling between frequency bands of interest. Any of these techniques has the potential to identify candidate predictors of tic onset.

Specific Analysis Approach for Aim 3: This protocol calls for testing an acute responsive DBS condition in subjects who reveal physiological predictors that can be set to sense tic by ECOG, and to respond to tic on the CM implanted device. It may also be possible to both sense and deliver stimulation from the CM DBS lead. Data will be analyzed using the Wilcoxon signed rank test. **We will collect physiology**

data and analyze the data, and test chronic responsive stimulation settings one month at a time for those subjects that respond well to the acute testion after Month 3.

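### The analysis section specifies no responsive-versus-continuous comparison for Aim 3, and the procedures attach the Aim 3 label to a comparison with pre-operative baseline

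*Combined protocol and SAP*

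**What the plan says.** Section 5 (Purpose), aim (3), sets out the hypothesis that "responsive brain stimulation will provide an alternative to chronic deep brain stimulation in TS". It gives the comparator for the acute test as "comparing the results of chronic continuous stimulation (Specific Aim 1) to an acute test of responsive stimulation". For the later chronic phase it says "Outcomes for chronic responsive stimulation will also be measured by comparing the results of chronic continuous stimulation". Moving a patient to that phase depends on a condition beginning "If acute responsive stimulation leads to low side effects and comparable clinical outcomes for a patient".

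Section 12 (Study Summary, Details of the Protocol), on the Month 6 conditions, uses the ON condition against pre-operative baseline for Aim 1. It then says that the "responsive stimulation response will be compared to the pre-operative baseline (specific aim 3").

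Section 13, Specific Analysis Approach for Aim 1, says "We will also perform comparisons of baseline to on/off/responsive conditions, and also comparisons of on/off conditions at six months as secondary analyses". The only difference between modes that it defines is this: "we will form paired difference scores of YGTSS (YGTSS on minus YGTSS off) at six months". The Specific Analysis Approach for Aim 3 says "Data will be analyzed using the Wilcoxon signed rank test" and names neither the two conditions to be paired nor the scale.

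Section 7 (Research Plan) describes the responsive work as exploratory.

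**The concern.** The aim concerns one mode relative to another. The only comparator that the procedures tie to Aim 3 by name is the pre-operative state, and section 13 never names responsive versus continuous. An analyst working from section 13 would have a test but no contrast. With three modes, a baseline and two tic scales (YGTSS and MRTRS), the contrast could be chosen after the data are seen.

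The baseline contrast cannot stand in for the missing one. Between the pre-operative rating and the Month 6 responsive rating, a patient has had surgery, has received months of continuous stimulation with repeated programming, and has a disorder that section 4 describes as fluctuating over time. All of these enter the change from baseline together with any effect of the responsive mode. Each mode is held for one hour before rating (section 12), and the plan does not discuss carry-over from the preceding mode. Improvement on baseline could therefore be seen whether responsive stimulation is as good as continuous stimulation, worse, or inactive.

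**Working it through.** **1. The statements side by side**

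| Place | Condition | Compared with | Scale | Label |
|---|---|---|---|---|
| Section 5, aim (3), acute test | Responsive | Continuous | not named | Aim 3 |
| Section 5, aim (3), chronic phase | Chronic responsive | Continuous | not named | Aim 3 |
| Section 12, Details of the Protocol | Responsive | Pre-operative baseline | not named | Aim 3 |
| Section 13, Aim 1 | ON, OFF, responsive | Baseline | not named for these secondary contrasts | Aim 1 secondary |
| Section 13, Aim 1 | ON | OFF | YGTSS | Aim 1 secondary |
| Section 13, Aim 3 | not named | not named | not named | Aim 3 |

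No section 13 row pairs responsive with continuous. Section 12 does not say that baseline is the only comparator, so it does not cancel section 5.

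**2. Are the data there?** Yes. Section 8 has blinded reviewers examine Month 6 videos in the continuous, OFF and responsive conditions. Section 12 has the statistician set a counterbalanced mode order and scramble the tapes. Under Specific Approaches for Aim 3, only patients with an identified predictor have a responsive setting at Month 6, so the number of pairs is at most 10 and is not known in advance.

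**3. What the named contrast could deliver.** The plan gives no power or precision figure for Aim 3, so there is none to reproduce. Inputs from section 13 are n ≤ 10, two-sided tests and alpha 0.05. My assumptions are normal paired differences, and n = 10, 8 or 6 patients with a predictor.

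The smallest attainable two-sided p-value for the signed rank test with n non-zero, untied differences is 2/2^n:
- n = 5: 2/32 = 0.0625, above 0.05
- n = 6: 2/64 = 0.031, below 0.05

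The MRTRS total is a sum of whole-number ratings, so zero differences can occur and the usual test drops them. The relevant count is therefore the number of non-zero differences, not the number of patients.

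Simulation of the exact test and of the matching Hodges-Lehmann interval, in units of the SD of the paired difference:

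| n | Mean half-width of exact 95% CI | Non-significant if the true difference is 1 SD | Non-significant if it is 0.5 SD |
|---|---|---|---|
| 10 | 0.71 | 21% | 72% |
| 8 | 0.89 | 39% | 81% |
| 6 | 1.27 | 64% | 89% |

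The contrast can be estimated, but only roughly. A non-significant result would be common even if responsive stimulation were clearly worse.

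**The case against.** The strongest reply is that nothing is contradicted. Section 5 states the continuous comparator twice, section 12 adds a baseline comparison without excluding it, and the Wilcoxon test in section 13 can be applied to the pair that section 5 names. The aim is exploratory and the data will exist anyway. Much of this stands, and it limits the point. Four stronger readings are not supported:

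- **A flat contradiction.** A reader might infer that sections 5 and 12 cannot both be followed. They can. What is missing is any statement of which comparison answers the aim, and its entry in section 13.
- **An Aim 3 result bound to be a change from baseline.** The Aim 3 paragraph in section 13 does not say baseline. The baseline-to-responsive comparison there is a secondary analysis listed under Aim 1.
- **An undefined non-inferiority claim.** The comparability wording in section 5 is a condition for moving an individual patient to chronic responsive testing. It is not a group-level inference, and nowhere does the plan propose to infer comparability from a non-significant p-value. The simulated percentages are a caution for the added contrast and do not describe an error already in the plan.
- **A quantified carry-over bias.** The documents give nothing from which to size carry-over after one hour in mode. It may exist and could make the modes look more alike; no more can be said.

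Figures 1 and 2 and a stretch of section 19 were not available. The statement about the missing contrast is limited to the text that was.

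What the reply does not meet is that the comparator labelled Aim 3 in the procedures cannot answer Aim 3, and that the contrast which can is absent from the analysis section.

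**Conclusion.** The point holds as an omitted contrast and an inconsistent label. Section 5 frames Aim 3 against continuous stimulation. Section 12 ties the responsive condition to pre-operative baseline under the Aim 3 label. Section 13 lists responsive only against baseline and leaves its Aim 3 test without a pair or a scale. A change from baseline cannot by itself show that responsive stimulation is an alternative to continuous stimulation.

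The consequence is confined to Aim 3, and the Aim 1 primary conclusion is unaffected. The textual finding needs no numerical assumption. The precision figures rest on normal paired differences and on assumed numbers of patients with a predictor. They show that even the right contrast will have wide intervals, so it should be presented as exploratory estimation. The correction should be made because it costs little and settles the contrast before the data are seen.

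**What to change.** Reconcile section 5 aim (3), the Month 6 conditions text in section 12, and section 13.

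1. In section 13, state that the Aim 3 contrast is the within-patient difference, responsive minus continuous ON, on the Month 6 test days, in patients with a predictor. Use one blinded scale scored in all three modes, for example the blinded-video MRTRS total averaged over the two raters.
2. Keep the Wilcoxon signed rank test, and report the matching Hodges-Lehmann estimate with its exact 95% CI.
3. If there are 5 or fewer non-zero differences, list the individual differences without a test.
4. Label the result as exploratory estimation, and state that a non-significant p-value will not be read as comparability. Add one sentence that one hour in mode may leave carry-over.
5. Keep responsive versus baseline as a descriptive comparison, and amend the section 12 clause to say so.
6. For chronic responsive stimulation (visits 6.1-6.4), name the continuous-stimulation visit that serves as reference.

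Responsive minus OFF, and ON minus OFF on the MRTRS, are optional additions.

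The cost is protocol and analysis wording plus one or two paired analyses on data already scheduled, with no extra visits or raters. The downside is wide intervals with at most 10 patients, which the report should state openly.

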(1) Test the hypothesis that centromedian (CM) continuous brain stimulation will be an effective and safe method for the treatment of tics in medication refractory TS. There is now a growing body of evidence supporting the use of DBS for tic suppression. Implantable brain stimulators provide a reversible and programmable solution to neuromodulation which are safer (no tissue destruction) and potentially more effective than ablative techniques such as thalamotomy, capsulotomy, and cingulotomy, especially because they can be performed bilaterally[62]. There are however important issues that may limit standard DBS effectiveness in this population including specific problems unique to this group of patients including the paroxysmal nature of the disorder. It would be desirable to design a therapy such as the one proposed in this grant application to neuromodulate only when needed (closed loop or responsive therapy). We plan to implant CM

thalamus and cortical ECOG bilaterally in 10 medication refractory TS subjects. We will employ a prospective blinded staggered onset design. We hypothesize that by using a chronic (continuous) stimulation strategy we will be able to achieve a greater than 40% reduction (over 6 months) in total tics (motor and phonic on the YGTSS) in more than $\frac{1}{2}$ of our subjects (6/10). We will in this study assess safety and also employ stopping rules to ensure subject safety.

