Power Analysis: We will determine the effectiveness of DBS by comparing total tic score (YGTSS) at the six month time point to the pre-operative value for each subject. A 40% or greater reduction will be considered a successful response. The power to detect a statistical significance between a null proportion of 0.10 (this assumes that the true proportion of successful responders is 10%). The power analysis revealed that for an alternative proportion of .60 (i.e., 6 of 10 patients will show a

40% or greater reduction in motor tics at six months) there is a statistical power of 0.80 at an alpha level of .05. Therefore, we anticipate ten participants will be required for this study. The *power* procedure in Statistical Analysis Software (SAS), version 9.1 was used to conduct the power analysis. Data collected from this study will provide additional and currently unavailable data to inform power analysis of subsequent studies in Table 2 below.

Table 2. Power Analysis for Sample Size Effects

Table Power Analysis		Sample Size					
		8 patients		9 patients		10 patients	
Alternative proportion	Number of responders	Power	Number of responders	Power	Number of responders	Power	
.30	2	0.25	3	0.27	3	0.29	
.40	3	0.39	4	0.43	4	0.46	
.50	4	0.54	5	0.59	5	0.63	
.60	5	0.70	5	0.75	6	0.80	

General Analysis Approaches: The Wilcoxon signed rank test will be used to test for significant pre-post changes in numerical measures (e.g., YGTSS). Spearman correlations will be used to test relationships among numerical measures (e.g., neurocognitive measures, severity of tics and quality of life measures). Both the Wilcoxon signed rank and Spearman correlation tests are nonparametric procedures that are robust from data departures from normality and appropriate in the case of small sample sizes. All statistical tests will be two-sided and will be considered significant if p-values are less than 0.05. SAS software will be used to conduct all data analysis.

Specific Analysis Approach for Aim 1: We will determine the effectiveness of the “on condition” of DBS by comparing motor tic score (YGTSS) at the six month evaluation to the pre-operative value for each subject. A 40% or greater reduction will be considered a successful response. We will then test the hypothesis that the proportion of successful responders is greater or equal to (6/10) using the exact

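### The stated power of 0.80 and Table 2 do not come from the planned one-sample exact binomial test: against the 0.10 null the power is 0.945, and the Aim 1 test sentence does not name that null

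*Combined protocol and SAP*

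**What the plan says.** The power paragraph in section 13 introduces "The power to detect a statistical significance between a null proportion of 0.10", sets the alternative at 0.60 (glossed as 6 of 10 patients responding), and reports that "there is a statistical power of 0.80 at an alpha level of .05". It concludes: "Therefore, we anticipate ten participants will be required for this study". "Table 2. Power Analysis for Sample Size Effects" gives powers for 8, 9 and 10 patients at alternatives of 0.30 to 0.60, each beside a number of responders. SAS's power procedure is cited, but the test and its options are not given.

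Under General Analysis Approaches, "All statistical tests will be two-sided and will be considered significant if p-values are less than 0.05". The Specific Analysis Approach for Aim 1 then tests whether "the proportion of successful responders is greater or equal to (6/10) using the exact" binomial test. That sentence does not mention 0.10.

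Section 6 separately requires 6 of 10 responders for the study to meet its effectiveness criteria. The design is one group of ten, each compared with his or her own pre-operative score; no comparator group is described.

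The score being counted also varies. Section 5 aims for a "greater than 40% reduction (over 6 months) in total tics (motor and phonic on the YGTSS) in more than" half of the subjects. Sections 7 and 12 also make the total tic score primary, while section 6 and the Aim 1 analysis use the motor score.

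**The concern.** The sample size rests on one power figure, and that figure should belong to the test that will be run. A one-sample exact test of 0.60 against 0.10 with ten subjects should have power well above 0.80, so either the calculation used a different test or the inputs are misreported.

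Two things are at stake. First, a reader may take 0.80 as the chance that the trial succeeds. It is neither the power of the primary test nor the chance of reaching 6 of 10. Second, the primary test's null is not fixed where the test is specified. Read literally, the Aim 1 sentence points to 6/10. If 0.60 were the null, the trial's own target result would count as no evidence of effect; against 0.10 the same result is decisive.

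**Working it through.** **Inputs (section 13):** n = 10 in one group, null 0.10, alternative 0.60, alpha 0.05 two-sided, exact binomial test. Stated power: 0.80.

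**Formula:** P(X ≥ c | p) = Σ over k = c to n of C(n,k) p^k (1−p)^(n−k).

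**1. Trying to reproduce 0.80.** Under the 0.10 null with n = 10, P(X ≥ 3) = 0.0702 and P(X ≥ 4) = 0.0128. The critical value is therefore 4, whether the test is one-sided at 0.05, uses 0.025 per tail, or uses the minimum-likelihood two-sided p-value. Power at 0.60 is P(X ≥ 4 | 0.60) = 0.945, so the stated figure is not reproduced.

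**2. Does any cut-off, and so any null, give 0.80?**

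| Cut-off c | 3 | 4 | 5 | 6 | 7 |
|---|---|---|---|---|---|
| P(X ≥ c of 10), true rate 0.60 | 0.988 | 0.945 | 0.834 | 0.633 | 0.382 |

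None does. One-sample normal approximations for the same cell run from 0.898 to 0.987 without continuity correction, and from 0.828 to 0.971 with it.

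**3. Table 2 against the exact test** (null 0.10, 0.025 per tail; the critical value is 4 for each n):

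| n | Source | 0.30 | 0.40 | 0.50 | 0.60 |
|---|---|---|---|---|---|
| 8 | Table 2 | 0.25 | 0.39 | 0.54 | 0.70 |
| 8 | exact, ≥4 | 0.194 | 0.406 | 0.637 | 0.826 |
| 9 | Table 2 | 0.27 | 0.43 | 0.59 | 0.75 |
| 9 | exact, ≥4 | 0.270 | 0.517 | 0.746 | 0.901 |
| 10 | Table 2 | 0.29 | 0.46 | 0.63 | 0.80 |
| 10 | exact, ≥4 | 0.350 | 0.618 | 0.828 | 0.945 |

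Across all cut-offs, only one of the twelve stated powers (n = 9, 0.30) equals an exact upper tail to two decimals. The n = 8 row depends on the two-sided convention. With the minimum-likelihood p-value, 3 of 8 rejects (p = 0.038) and the row becomes 0.448/0.685/0.855/0.950. The n = 9 and n = 10 rows are the same under both.

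**4. The responder column.** Sample size times alternative gives 2.4/3.2/4.0/4.8 for n = 8, 2.7/3.6/4.5/5.4 for n = 9 and 3/4/5/6 for n = 10. Rounded, these are the listed counts in all twelve cells. The column holds expected counts, not critical values.

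**5. The 6-of-10 criterion.** P(X ≥ 6 of 10) at true rates 0.30/0.40/0.50/0.60 is 0.047/0.166/0.377/0.633. At 0.60, the chance of exactly 4 or 5 responders is 0.945 − 0.633 = 0.312; such a result rejects 10% but fails 6 of 10.

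**6. If 0.60 were read as the null.** P(X ≥ 8) = 0.167, P(X ≥ 9) = 0.046 and P(X = 10) = 0.006. Rejecting upward would need 9 of 10 one-sided, or 10 of 10 two-sided (the minimum-likelihood p for 9 of 10 is 0.059). An observed 6 of 10 gives p = 0.00015 against 0.10 (0.00029 if the tail is doubled), but a one-sided p of 0.63 against 0.60.

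**Aside, inferred only.** A one-sided pooled comparison of two independent groups, with n patients per group, comes within 0.006 of every Table 2 cell (0.794 for the headline cell). The documents do not say this was used, and the plan has neither a second group nor a one-sided test.

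**The case against.** The strongest reply is that the error is conservative. Against 0.10 the power is understated, so ten subjects remain enough. By the exact test even six would give 0.82 at 0.60 (3 or more responders, size 0.016), although exact power does not rise steadily with n. This stands, and it means the correction does not call the enrolment target into question.

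Second, section 13 names 0.10 as the null and 0.60 as the alternative shortly before the Aim 1 sentence, so 6/10 there can be read as the alternative, and no passage mentions needing 9 or 10 responders. That is the more natural intent. The sentence as written still attaches 6/10 to the hypothesis under test and gives neither a null nor a critical value, so the doubt remains until a sentence removes it.

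Third, demanding 6 of 10 on top of statistical significance is a legitimate choice: six responders always reject 10%, so the two rules are nested. Agreed. What is missing is any stated probability of meeting the stricter rule.

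Finally, the total-versus-motor conflict is a separate matter of endpoint definition. It affects none of these figures and adds no weight here.

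**Conclusion.** The point holds. For n = 10 and a 0.10 null, the planned test has power 0.945 at 0.60, not 0.80, and eleven of the twelve powers in Table 2 match no exact binomial upper tail. The stated 0.80 is too low for the test against 10% by about 0.145. If taken as the chance of reaching 6 of 10, it is too high by about 0.17 (0.80 − 0.633).

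The n = 10 result rests only on the single-group design, the exact binomial test and the 0.10 null, and it does not depend on sidedness. Only the n = 8 row needs an assumption about the two-sided convention. The consequences of a 0.60 null apply only if the Aim 1 sentence is read literally. The point must be fixed because the figure behind the sample size does not belong to the primary test, and that test's null is not stated where the test is specified.

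**What to change.** 1. In the Aim 1 analysis, state that the exact binomial test uses the 0.10 null, or name another null and recompute. Give the two-sided convention and the critical value (4 of 10 for 0.10). Say that 6 of 10 is a separate effectiveness criterion, and whether it is judged on the total or the motor YGTSS score. If another null is preferred, then with 0.025 per tail and n = 10, nulls of 0.122–0.187 give a critical value of 5, and 0.188–0.262 give 6.
2. If 0.10 is kept, replace the powers in Table 2 with the exact values shown in the working, stating the convention used for n = 8. Show critical values instead of rounded expected counts, and add a row for 6 or more of 10: 0.05/0.17/0.38/0.63.
3. Replace the single 0.80 with both figures, for example: *With 10 subjects and a true responder rate of 0.60, the exact binomial test rejects a 10% rate (4 or more responders, actual size 0.013) with power 0.945; the separate criterion of 6 or more of 10 is met with probability 0.63.*

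Optionally, add the precision of a 6-of-10 result (exact 95% CI 26% to 88%). The cost is one recomputed table and two or three sentences; enrolment and study conduct do not change.

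### Section 13 attaches an unadjusted two-sided 0.05 significance claim to open-ended Wilcoxon and Spearman families, without labelling the clinical correlations exploratory

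*Combined protocol and SAP*

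**What the plan says.** Section 13, General Analysis Approaches, plans Wilcoxon signed rank tests for pre-post change in numerical measures, with the YGTSS as the only example. It adds that "Spearman correlations will be used to test relationships among numerical measures", naming neurocognitive, tic-severity and quality-of-life measures as examples. It closes with the decision rule: "All statistical tests will be two-sided and will be considered significant if p-values are less than 0.05".

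Other parts of the plan are more specific:

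- **Primary and secondary outcomes.** Section 12 (Study Summary) names one primary effectiveness outcome, a YGTSS responder criterion at six months, and one secondary effectiveness variable, the blinded MRTRS ratings. Section 13 (Aim 1) assigns the primary outcome an exact binomial test and then says "We will also perform comparisons of baseline to on/off/responsive conditions", together with an on-versus-off comparison. It calls these secondary.
- **Aim 2.** Section 13 describes the first physiology techniques as exploratory. The Specific Approaches for Aim 2 mention a prior limit on the number of analysis methods.
- **Aim 3.** Predictors are selected within subject at p < 0.1, with a stated reason. The responsive condition is analysed by the Wilcoxon test.

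In the text available for review, the clinical Spearman correlations and the remaining pre-post Wilcoxon tests get no such treatment.

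**The concern.** The plan is not silent here. It states a rule under which any Wilcoxon or Spearman result below 0.05 is to be called significant, while the set of tests is left open. The instruments are numerous: a broad cognitive battery, several tic scales, eight SF-36 scales and five QOLAS domains, many repeated over visits. A report that follows the rule can present chance results as significant, and the reader cannot tell from how many tests they came.

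The sample size adds a second problem. Section 13 states: "Therefore, we anticipate ten participants will be required for this study". At that size only large coefficients can pass, so the results selected for emphasis will overstate the associations. Section 13 also says the data should inform the power analysis of later studies. Coefficients selected in this way would be poor inputs for that.

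**Working it through.** **The plan's own figure.** There is none on this point: no number of tests and no expected number of chance findings. The stated power of 0.80 concerns the responder analysis only.

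**Step 1. Inputs.** From the documents: two-sided 0.05 per test and n = 10 (section 13); SF-36 with 8 scales and QOLAS with 5 domains (section 7); the cognitive tests in Table 1; the battery given before surgery and at about one year (section 8). Assumed, because the plan does not fix which scores enter the correlations:

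- C, cognitive scores: 10 to 16, leaving out the WASI-II and the mood scales
- T, tic scores: 2 to 5, from YGTSS motor, phonic and total, MRTRS and PUTS
- Q, quality-of-life scores: 2 to 13

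**Step 2. Pairs and expected chance findings at one time point.** Pairs k = C×T + C×Q + T×Q. If all true correlations are zero, the expected number passing is 0.05 × k, whatever the dependence between tests.

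| C, T, Q | k | 0.05 × k |
|---|---|---|
| 10, 2, 2 | 20 + 20 + 4 = 44 | 2.2 |
| 11, 3, 9 | 33 + 99 + 27 = 159 | 8.0 |
| 12, 4, 10 | 48 + 120 + 40 = 208 | 10.4 |
| 14, 5, 13 | 70 + 182 + 65 = 317 | 15.9 |
| 16, 5, 13 | 80 + 208 + 65 = 353 | 17.7 |

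For a round 200 pairs the figure is 10.0. Even at 44 pairs, if the tests were independent, the chance of at least one false positive is 1 − 0.95^44 = 0.895.

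**Step 3. Dependence.** Scores within a domain are likely to be correlated. That leaves the mean almost unchanged but widens the spread. Simulation for 208 pairs at n = 10 gives a 95% range of 5 to 17 with independent scores, 4 to 19 with within-domain correlation 0.3, and 1 to 29 with 0.6.

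**Step 4. Tic by quality-of-life pairs.** A zero correlation is least credible here, since the inclusion criteria themselves link severe tics to disrupted quality of life. Dropping T×Q leaves 44 − 4 = 40 to 353 − 65 = 288 pairs, or 2.0 to 14.4 expected chance findings.

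**Step 5. What passing means at n = 10.** From the exact permutation distribution (10! = 3,628,800 orderings), |rho| ≥ 0.648 has two-sided size 0.0490. The next attainable value, 0.636, has size 0.0544. It would pass only under the t approximation. So any coefficient that passes is at least about 0.64 to 0.65. The approximate Fisher interval at 0.648 shows how little that establishes: atanh(0.648) = 0.772 and 1.96/√7 = 0.741, giving limits tanh(0.031) = 0.03 and tanh(1.513) = 0.91.

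**Step 6. Wilcoxon tests.** The documents give no count. As an illustration, take the schedule of assessments through Month 24, each SF-36 scale and QOLAS domain tested separately, and one score for each other scale. YGTSS, MRTRS and SF-36 at nine post-operative visits give 9 + 9 + 72. HAM-D, Y-BOCS, QOLAS, YMRS and CAARS at four visits give 4 + 4 + 20 + 4 + 4. The total is 126 tests before any cognitive score. Some of these would reflect real change, so no chance count is drawn from them.

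**The case against.** The strongest reply is that this is a ten-subject, single-arm early study with one distinguished primary outcome. Unadjusted p-values for supporting analyses are common at this stage. No effectiveness criterion, safety outcome or stopping rule depends on a correlation p-value. Any count of correlations is the reviewer's own, and nothing in the plan says every pair will be tested.

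Much of this stands, and it rules out several stronger readings that a reader might infer:

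- **That about ten false findings will occur.** The documents give no count. Ten needs both some 200 tests and no true correlation among them.
- **That the count follows from having ten subjects.** At a fixed 0.05 the expected count hardly depends on n. The small sample affects how large the passing coefficients look.
- **That every test is held to 0.05, or is declared significant.** Tests are judged at 0.05, and the Aim 3 predictors use p < 0.1.
- **That secondary findings rank with the primary.** Sections 12 and 13 separate the primary outcome from the secondary comparisons.
- **That the primary result is compromised.** The binomial test's own error rate does not change because other tests are run.

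The reply does not remove the sentence in section 13. An early study can reasonably leave its exploratory tests unadjusted, but this plan also calls them significant, and it does not label the clinical correlations exploratory as it does the first Aim 2 techniques.

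**Conclusion.** The point holds as a matter of labelling and reporting. The plan attaches an unadjusted significance claim to test families that it neither lists nor counts. About 2 to 18 chance findings among the correlations at one time point is a conditional illustration. It rests on the assumed 44 to 353 pairs, on all pairs being tested and on every true correlation being zero. The cutoff of about 0.65 at n = 10 does not rest on those counts. It does assume complete data on ten subjects.

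No adjustment method is called for. Bonferroni over 200 tests, for example, would require p < 0.05/200 = 0.00025, or |rho| of at least about 0.93 at n = 10, which would leave the correlations with almost no use. Severity is low: the primary conclusion is untouched and the repair is cheap.

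**What to change.** Replace the closing sentence of General Analysis Approaches in section 13 so that it does the following:

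- Limits the two-sided 0.05 significance claim to the primary binomial test and to the secondary and Aim 3 comparisons the protocol already names. These are the blinded MRTRS ratings (section 12, Study Summary) and the on, off and responsive comparisons (section 12, Details of the Protocol, and section 13, Aims 1 and 3).
- Describes the secondary and Aim 3 results as supportive of the primary result.
- Labels all other Wilcoxon analyses and all Spearman analyses exploratory. These are reported as estimates with confidence intervals and unadjusted p-values, without being called significant.
- Requires the report to state how many exploratory tests were run in each family.
- Notes that the p < 0.1 rule for Aim 3 predictors is separate, so that the new sentence does not contradict it.

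No fixed-order testing procedure is required. The blinded MRTRS variable and the Aim 3 analysis keep their place in the plan. The change needs no extra data, visits or subjects. Its cost is that fewer results may be called significant.
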